### **Sample size calculation**

There is no previous studies available specifically on the use of inversion recovery sequences.

Based on previous paper by deSantis et al. with use of 7T MRI the pickup rate of MRI on patients with previous negative MRI would be around 30%. We prudently estimate that as the current MRI, the pick up rate would be lower than an even-higher resolution 7T MRI and approximately at half of previous study quoted (i.e. 15%), and a 5% false negative rate on patients who actually had lesions on previous baseline MRI. With a 80% statistical power and two-tail alpha = 0.05, approximately 22 patients who needs to have both MRI done and undergone surgery. And assuming that only 1/3 of patients who had workup will undergo surgery, approximately 66 patients are required.

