#### Statistical analysis protocol

The primary outcome of the study is the sensitivity and specificity of the baseline MRI (bMRI) and the high-resolution MRI (hrMRI) studies, based on the standard of surgical findings on patients who underwent either intracranial EEG or surgical resection. Each of the sensitivity and specificity of the

two tiers of MRI studies (baseline MRI and high-resolution MRI) will be compared with use of contingency table and chi-square test.

The secondary outcomes would include the following:

- Number of cases with true positive, and false positive findings on bMRI or hrMRI; and descriptive statistics of findings in patients who had MRI but did not undergo surgery.
- Inter-observer and Intra-observer agreement for findings on bMRI or hrMRI by kappa statistics.

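### The 80% power is stated for 22 operated patients, but sensitivity and specificity each use only part of them, and the protocol sizes neither part

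*Protocol*

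**What the plan says.** The protocol's "Sample size calculation" section sets the operating characteristics as "With a 80% statistical power and two-tail alpha = 0.05" and concludes that the study needs "approximately 22 patients who needs to have both MRI done and undergone surgery". It then scales up to recruits: "assuming that only 1/3 of patients who had workup will undergo surgery, approximately 66 patients are required". It says nothing about how many operated patients are expected to have a positive or a negative reference result.

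The "Statistical analysis protocol" section defines the endpoint: "The primary outcome of the study is the sensitivity and specificity of the baseline MRI (bMRI) and the high-resolution MRI (hrMRI) studies". The reference is "based on the standard of surgical findings on patients who underwent either intracranial EEG or surgical resection". The two measures are each to be compared between the baseline and the high-resolution MRI.

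**The concern.** The sample size section counts operated patients. The primary analysis does not use operated patients as one group: it splits them by reference result. Reference-positive patients form the denominator for sensitivity and reference-negative patients the denominator for specificity. The conversion from recruits to analysed patients therefore stops one step early.

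If 22 is meant as the denominator for sensitivity, every operated patient has to be reference-positive, and specificity then has no denominator. If some are reference-negative, as a primary specificity analysis requires, sensitivity rests on fewer than 22 of any 22 operated patients and specificity on the small remainder. Either way, the stated 80% is attached to a group on which neither primary measure is computed. A reader would take both measures to be adequately sized, when the size of the specificity comparison is not addressed at all.

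**Working it through.** **Inputs from the protocol.** Operated patients needed: 22. Share of recruits operated: 1/3. Recruits: 66. All three are in "Sample size calculation".

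**Inputs assumed.** q, the share of verified patients who are reference-positive, is not in the documents; 0.9, 0.8 and 0.7 are used as a range. The verified share s is 1/3 on the plain reading. An alternative of 0.40 is an assumption, used to see what happens if intracranial EEG patients are additional.

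**Step 1: the plan's own figure.** 22 / (1/3) = 66. The multiplication reproduces exactly.

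**Step 2: expected denominators from 66 recruits.** Reference-positive = 66 × s × q; reference-negative = 66 × s × (1 − q). At s = 1/3 the verified total is 22:

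- q = 0.9: 22 × 0.9 = 19.8 positive, 22 × 0.1 = 2.2 negative
- q = 0.8: 22 × 0.8 = 17.6 positive, 22 × 0.2 = 4.4 negative
- q = 0.7: 22 × 0.7 = 15.4 positive, 22 × 0.3 = 6.6 negative

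**Step 3: chance of at least 22 reference-positive patients.** The count is taken as Binomial(66, s × q). At s = 1/3:

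| q | s × q | P(at least 22) |
|---|---|---|
| 1.0 | 0.333 | 54.6% |
| 0.95 | 0.317 | 43.1% |
| 0.9 | 0.300 | 31.9% |
| 0.8 | 0.267 | 13.9% |
| 0.7 | 0.233 | 4.2% |

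The probability falls below one half once q is below about 0.98. A single reference-negative patient among 22 corresponds to q = 21/22 = 0.955, which is already below that point (44%).

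**Step 4: if the verified share is larger.** At s = 0.40 the expected verified total is 66 × 0.40 = 26.4:

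| q | Expected positive | Expected negative | P(at least 22 positive) |
|---|---|---|---|
| 0.9 | 23.8 | 2.6 | 72% |
| 0.8 | 21.1 | 5.3 | 45% |
| 0.7 | 18.5 | 7.9 | 20% |

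The sensitivity denominator improves. The specificity denominator stays below eight in expectation throughout.

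**Step 5: can the loss be expressed as power?** Not from the protocol's own inputs. Its 15% pickup and 5% false negative rates, read as the two discordant rates of a paired comparison, give about 17% power at 22 patients, so there is no reproducible 80% to start from. The working therefore stays with denominators, which do not depend on how the 22 was obtained.

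**The case against.** **The conversion contains no arithmetic error.** That is right. It is exact, and both the 22 and the 66 are given as approximate. A reader might infer that using an average yield is itself the fault. It is not: sizing on an expected count is ordinary practice, and at q = 1 the chance of reaching 22 is slightly better than even. The gap is the missing split by reference result.

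**The 66 is not a fixed stop.** A reader might infer that recruitment ends at 66 whatever the surgical yield. The protocol does not say so. The stated need is 22 operated patients, and 66 is derived from it through a stated share.

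**The verified group may be larger than a third.** The one third counts surgery, whereas the reference standard covers intracranial EEG or resection. The protocol calls the standard surgical findings, so the plain reading places both within the third, but this is not settled. If they are additional, the chance of 22 reference-positive patients can exceed one half (72% at q = 0.9 and a 40% verified share). An unqualified statement that 66 recruits will probably fall short is therefore too strong.

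**q may be close to 1.** Entry requires drug-resistant focal epilepsy with a probable site supported by two concordant sources, so a high q among operated patients is plausible. But a high q makes the specificity problem worse, and the protocol names specificity as primary and lists false positives among the secondary outcomes.

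**The unit of analysis is not stated.** Readers score the localization of the site. If the analysis were per site, negatives could come from the same patients and the split would not be a strict trade-off. The protocol's sizing is per patient, however, and gives no count of sites.

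**Conclusion.** The point holds in a limited form. The protocol makes two measures primary and attaches its size and power to a group that, counted per patient, is the denominator of neither.

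With one third verified and q assumed between 0.9 and 0.7, sensitivity would rest on about 15 to 20 patients and specificity on about 2 to 7. The chance of 22 reference-positive patients would be 32% down to 4%. If intracranial EEG patients add to the third, the chance is higher (72% down to 20% at an assumed 40% share). The thin specificity denominator remains under both readings.

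The size depends on q, on the verified share, on a per-patient analysis and on a binomial yield. No power loss is claimed, because the 22 does not follow from the stated 15% and 5%. That is a separate and larger problem, and correcting the 22 alone would leave this one in place: any new number multiplied by three would again count operated patients only.

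**What to change.** Restate the "Sample size calculation" section by the denominators that the primary analysis uses:

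1. State the expected verified share and say whether patients with intracranial EEG alone fall within the one third or are additional to it.
2. State q with its basis, or a range if there is none.
3. Give the expected reference-positive and reference-negative counts from 66 recruits.
4. Give the power or the expected precision for sensitivity and for specificity separately at those counts, using the corrected basis for the 22 once that is settled.

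The sponsor can keep 66 and report the lower figures. If it prefers to keep an expected 22 reference-positive patients at a one-third verified share, recruits needed are 22 / (q/3), rounded up: 74 at q = 0.9, 83 at 0.8 and 95 at 0.7.

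The cost is a few sentences in one section and probably a less favourable stated power. No study procedure changes. Items 1 to 3 can be written now; item 4 has to wait for the corrected derivation of the 22.

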### **MRI scanning**

Patient will be scheduled to be scanned at the Siemens Prisma 3T MRI scanner at MRI facility, the Chinese University of Hong Kong. The scanning protocol consists of the following staple sequences for evaluation of focal epilepsy:

- Axial, Coronal and Sagittal (left and Right) 2D T1-weighted inversion recovery sequences focusing on site of lesion.
- 3D FLAIR T2-weighted MRI whole brain with multi-planar reconstruction (MPR).
- 3D T1-weighted Sagittal MPRAGE (Magnetization Prepared - RApid Gradient Echo) with MPR.

The following sequences will be applied optionally depending on the site of clinical suspicion and whether dedicated mapping will be required:

- Diffuse tensor imaging of whole brain (DTI)
- Functional MRI (fMRI) for mapping of specific cortical function close to the suspected site of lesion.
- Oblique coronal T2-weighted sequences of the hippocampus if suspected hippocampal sclerosis.
- Thin-cut dedicated T2-weighted or proton-density weighted images.

Contrast injection is usually not required unless otherwise clinically needed (e.g. for scanning of additional clinical indications).

The basic sequences will take approximately 30minutes, and the optional sequences (if needed) would be variable, the whole protocol will be completed within 1 hour.

All high-resolution MRIs performed under this study will be reported by board-certified radiologist and be available on patient's electronic health records (ePR).

#### Image interpretation

The baseline MRI of the patients will be retrospectively reviewed, while the MRI performed in this study will also be reviewed by two different radiologists. Radiologists are not blinded to the clinical history and site of clinical suspicion but are blinded to the subsequent surgical findings and outcomes.

The localization of the site of epilepsy will be pointed out according to a five-point confidence scale (1: very unlikely, 2: unlikely, 3: equivocal/ suspicious, 4: likely, 5: highly likely).

A likelihood score of 3 or above would indicate a positive imaging study.

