### **Patient recruitment**

**Inclusion:** Consecutive patients with drug-resistant focal epilepsy fulfilling the following criteria –

1. Diagnosis of focal epilepsy with a probable site identified, as defined by concordant results from any TWO of the following:
  - Clinical seminology compatible with focal epilepsy.
  - Electroencephalopathy pointing towards a specific site for focal epilepsy.
  - Positive ictal brain scintigraphy with SPECT-CT correlation.

AND

2. Previous MRI (at least one study with protocol tailored for epilepsy) which did not reveal accountable focal lesion.

AND

3. Able to consent for MRI examination (if patient under age of 18, consent for MRI will be obtained from guardian). Patients will be provided information leaflets to read on, and written consent before taking part in this study and MRI examination.

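### The masking rule leaves out the other MRI and reader assignment is unclear, so the baseline versus high-resolution comparison can be biased

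*Protocol*

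**What the plan says.** **Masking.** Under Image interpretation: "Radiologists are not blinded to the clinical history and site of clinical suspicion but are blinded to the subsequent surgical findings and outcomes". No section states a reading order, separate sessions or a washout.

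**Readers.** The same section says: "The baseline MRI of the patients will be retrospectively reviewed, while the MRI performed in this study will also be reviewed by two different radiologists". The Statistical analysis protocol adds a secondary outcome: "Inter-observer and Intra-observer agreement for findings on bMRI or hrMRI by kappa statistics".

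**Positivity.** Each scan is scored on a five-point confidence scale. "A likelihood score of 3 or above would indicate a positive imaging study", and 3 is the equivocal or suspicious category.

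**What is known or accessible.** Inclusion criterion 2 requires an earlier epilepsy-protocol MRI "which did not reveal accountable focal lesion". Under MRI scanning, "All high-resolution MRIs performed under this study will be reported by board-certified radiologist", and the report goes into the electronic patient record. Handling and Storage of personal data says that the images can be viewed on hospital clinical workstations. It also says that MRI data are anonymised and encrypted before research analysis, which is done on those workstations too.

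**Use.** The primary outcome is sensitivity and specificity of each scan against surgical findings, in patients who had intracranial EEG or resection. The "two tiers of MRI studies (baseline MRI and high-resolution MRI) will be compared with use of contingency table and chi-square test".

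**The concern.** Masking readers to surgery protects each scan's reading from the reference standard. It does not protect one scan's reading from the other, and the primary outcome is a comparison of the two scans in the same patients. A radiologist who has seen a lesion on the hrMRI, or its report, may find a faint correlate when re-reading the bMRI. That correlate need only reach the equivocal score of 3 to count as positive.

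Reader assignment raises a second problem. If different people score the two scans, a difference in personal threshold cannot be told apart from a difference between scans.

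Both act at the reading stage, so later analysis cannot undo them. A team could read the two scans side by side and still comply with the section as written.

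**Working it through.** **Step 1. What the masking rule covers.**

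- Clinical history and suspected site: stated, known to readers.
- Surgical findings and outcomes: stated, masked.
- Images and report of the other MRI: not stated.
- The other reader's score: not stated.
- Earlier MRI negative: not stated as masked, and known for every patient from inclusion criterion 2.

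**Step 2. Whether another section closes the gap.** Anonymisation removes identity but is not described as hiding one scan from the reader of the other. Research analysis also takes place on the type of workstation where the clinical images can be viewed. The kappa analysis suggests more than one reader and repeat reads, possibly on both scans, but it assigns nobody and masks nothing.

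**Step 3. What the reader sentence can mean.** There are three possible readings:

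1. Two radiologists for the hrMRI only.
2. The same two for both scans.
3. Different radiologists for each scan.

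The kappa outcome makes the first less likely, but the text does not settle it. Only the second separates reader from scan.

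**Step 4. Direction.**

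- Seeing the hrMRI before re-reading the bMRI tends to raise bMRI sensitivity and shrink the difference. If the hrMRI call was a false positive, the same hindsight could lower bMRI specificity.
- A lower reader threshold on the hrMRI would raise its sensitivity and lower its specificity. A lower threshold on the bMRI would do the reverse.

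The direction is therefore not fixed.

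**Step 5. How many reads matter.** The Sample size calculation gives 66 patients with one third operated: 66 / 3 = 22, which agrees with the stated 22. (The 22 itself does not reproduce from 15% versus 5% at 80% power and two-sided 0.05: the unpaired formula gives 141 per group and the paired formula 155 pairs. That is a separate matter, and 22 is taken here as given.)

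*Effect on the estimate.* Sensitivity uses only operated patients with a lesion and specificity only those without, so each denominator is at most about 22. One shifted patient-level call on one scan moves the relevant difference by at least 1/22 = 4.5 percentage points. The protocol's assumed pick-up rate is 15%.

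*Effect on significance.* The protocol names a chi-square test. Exact McNemar is used here for illustration because both scans come from the same patients. If all *d* discordant pairs favour the same scan, the two-sided p-value is 2 × 0.5^*d*:

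- d = 5: 2 × 0.5^5 = 0.0625
- d = 6: 2 × 0.5^6 = 0.031
- d = 7: 2 × 0.5^7 = 0.016

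If six patients are positive on hrMRI only and one bMRI score moves from 2 to 3, the pairs fall from 6 to 5 and significance at 0.05 is lost. From 7 pairs it takes two such shifts. One call shifted the other way takes 5 to 6 and creates significance.

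*Limit of the illustration.* At the assumed 15% pick-up with none on bMRI, 22 patients give an expected 22 × 0.15 = 3.3 discordant pairs, below 6 before any reading bias. The calculation shows how sensitive the result is to single reads. It does not predict the trial's result.

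**The case against.** The strongest reply is that silence is not a rule. Nothing in the protocol describes same-session or unmasked reading, a site could read the scans independently and comply, and reading order, washout and score locking are often set in a reading manual or SAP, neither of which is at hand. This stands to the extent that the comparison can be biased, not that it will be. It does not remove the point, because the protocol itself sets out the masking rule and leaves out the item on which a paired scan comparison depends.

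A reader might infer several stronger claims that the documents do not support:

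- **That two radiologists are assigned to the hrMRI alone.** The sentence is ambiguous, and the kappa outcome points towards several readers on both scans. Only unclear assignment can be claimed.
- **That readers will open the hrMRI report in the record.** Anonymisation before analysis makes this less certain, although it is not stated as masking.
- **That power would fall sharply.** If 15% one-directional discordance were halved by hindsight to 7.5%, exact McNemar power over 66 patients would fall from 94% to 38%. The primary outcome is restricted to about 22 operated patients, where the same figures are 10% and 0.5%. Power there is low before any hindsight, and the halving is an assumption with no source in the protocol.
- **That knowing the earlier scan was negative inflates the difference.** If bMRI detection is taken as 0%, such anchoring has nothing to lower.
- **That masking earlier reports would cure everything.** Inclusion criterion 2 tells every reader who knows the study that an earlier MRI was negative.

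**Conclusion.** The point holds in limited form. The stated masking rule omits the other MRI and its report, reader assignment across the two scans is unclear, and no other section of the protocol repairs either. With a retrospective bMRI re-read, hrMRI results in the patient record and an equivocal score counted as positive, the primary comparison can be biased.

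The direction and size cannot be determined from the protocol. What can be said, taking about 22 operated patients as planned, is that one or two shifted calls can matter. The effect on the estimate rests on one call per scan per patient; the effect on significance also assumes that all discordance runs in one direction and that an exact McNemar test is used. The rule should be completed before study reading begins.

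**What to change.** Amend the Image interpretation section to state that:

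- the same two radiologists independently score both the bMRI and the hrMRI of every patient;
- the two scans are read in separate sessions, in random order, with a washout (for example at least 4 weeks, a suggested figure and not one from the protocol);
- each reader is masked to the other scan's images and report and to the other reader's score;
- the same clinical history and suspected site are supplied for both reads;
- scores are locked before the other scan is opened;
- one rule for combining the two readers applies to both scans.

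The section should also acknowledge that readers cannot be masked to scan type, since the images differ, or to the entry criterion of an earlier negative MRI.

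Formal clinical reporting of the hrMRI can continue unchanged, with the research scores recorded separately. The cost is protocol wording, scheduling of two sessions and a longer reading period. No extra scans or patients are needed, and no readers beyond the two radiologists already named.

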## **Study protocol**

This study will be a prospective cohort model comparing baseline MRI and high-resolution MRI in delineation of focal abnormalities accounting for epilepsy.

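### The reading scale scores confidence in the epilepsy site, not in a visible lesion, so the positivity rule permits a positive scan from the known clinical history alone

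*Protocol*

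**What the plan says.** Four parts of the protocol bear on this.

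- **Target.** The Study protocol section sets out to compare the two MRIs in "delineation of focal abnormalities accounting for epilepsy". The entry criterion on earlier imaging (Patient recruitment, inclusion criterion 2) uses the same idea: a previous epilepsy-protocol MRI "which did not reveal accountable focal lesion".
- **Scored item and threshold.** Under Image interpretation, "The localization of the site of epilepsy will be pointed out according to a five-point confidence scale". The scale runs from very unlikely (1) to highly likely (5), with 3 labelled equivocal or suspicious. The rule is then: "A likelihood score of 3 or above would indicate a positive imaging study".
- **What readers know.** "Radiologists are not blinded to the clinical history and site of clinical suspicion but are blinded to the subsequent surgical findings and outcomes". Inclusion criterion 1 guarantees that there is a site to know: "Diagnosis of focal epilepsy with a probable site identified, as defined by concordant results from any TWO of the following". The sources are semiology, EEG and ictal SPECT.
- **Use of the call.** The Statistical analysis protocol makes sensitivity and specificity of baseline MRI (bMRI) and high-resolution MRI (hrMRI) the primary outcome. Both are judged against surgical findings in patients who had intracranial EEG or resection.

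**The concern.** The study asks whether an MRI shows a lesion. The scale asks how confident the reader is about where the epilepsy arises. These are different questions in this population, because a probable site has been established without MRI in every patient and the reader has been told what it is.

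Suppose a reader sees nothing abnormal but knows that semiology and EEG agree on one region. That reader could rate the site as likely (4) without breaking any stated rule, and the scan would be recorded as a positive MRI. Even a 3 would be enough.

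To the extent that this happens, the primary endpoint measures the entry criterion again rather than what the MRI adds. Positives that come from the history can occur on either scan. They would raise apparent sensitivity, lower specificity, and alter the bMRI–hrMRI contrast that the study is built to estimate.

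**Working it through.** **1. Text check.** The protocol gives no figure for this rule, so there is none to reproduce. The first question is whether any sentence ties a positive score to something seen on the images. Image interpretation gives the item, the five labels, the threshold and the blinding, and none of these mentions a visible abnormality. The other sections name a lesion or abnormality as the target but do not define a positive score. The permission is therefore real on the wording.

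**2. Illustration of size.** Inputs:

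- v_h, the visible-lesion rate on hrMRI: 15%, the pick-up rate that the protocol's Sample size calculation takes as half of 30%. Using it as a sensitivity is an assumption.
- v_b, the visible-lesion rate on bMRI: 0%. This is an assumption, prompted by the entry requirement of a previous negative MRI.
- s, the share of scans without a visible lesion that score 3 or above from the history alone. The documents do not give it, so a range is shown.
- s is taken to be the same for both scans and for reference-negative patients. This is an assumption.

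Observed sensitivity = v + (1 − v)s. For bMRI this is s; for hrMRI it is 0.15 + 0.85s.

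Difference = (1 − s)(v_h − v_b) = 0.15(1 − s).

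Specificity is at most 1 − s. It is lower still if some reference-negative scans show a misleading abnormality.

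| s | bMRI sensitivity | hrMRI sensitivity | Difference (points) | Specificity at most |
|---|---|---|---|---|
| 0% | 0% | 15% | 15 | 100% |
| 10% | 10% | 15 + 8.5 = 23.5% | 13.5 | 90% |
| 25% | 25% | 15 + 21.25 = 36.25% | 11.25 | 75% |
| 50% | 50% | 15 + 42.5 = 57.5% | 7.5 | 50% |

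**3. Unequal s.** With v_b = 0 and separate shares s_b and s_h, the difference is 0.15 + 0.85s_h − s_b.

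- s_b = 10%, s_h = 25%: 0.15 + 0.2125 − 0.10 = 0.2625. The gain widens to 26.25 points.
- s_b = 25%, s_h = 10%: 0.15 + 0.085 − 0.25 = −0.015. The gain becomes a deficit of 1.5 points.

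The shrinkage in the table is thus a consequence of equal s and not a general result.

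**The case against.** The best reply is that the sentence is loosely worded but its intent is clear. It stands under a heading about interpreting images, it ends in a verdict on the imaging study, and the Statistical analysis protocol speaks of findings on each MRI. If knowing the site were enough for a 4, almost every scan would be positive, including baseline MRIs that the protocol itself treats as negative. Readers may therefore score only what they see, and s may be near zero. This stands as a limit on the size of the problem. It does not supply the missing condition, and two readers could apply the item differently.

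A second reply is that a site-based score suits patients whose reference is intracranial EEG, which locates seizure onset rather than showing a lesion. That is a reason to record location, which the fix below does. It is not a reason to let a scan with nothing visible count as positive.

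A third is that reading-form detail may sit in a SAP or reading manual. That is true of lists of qualifying abnormalities, but the protocol itself fixes the item, threshold and blinding.

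Three stronger readings are tempting, and the documents do not support them:

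- *That both sensitivities are in fact inflated and the contrast in fact shrinks.* This depends on s, which is unknown, and the direction for the contrast depends on s being equal on both scans.
- *That a history-driven score would usually match the reference site because surgery is planned from the same clinical information, so a site-matching rule could not help.* The protocol does not say how the surgical or intracranial EEG site is chosen. Under Handling and Storage of personal data it says that the study images are also used for surgical navigation planning.
- *That telling readers the clinical site is itself an error.* It mirrors clinical reading. The weakness lies in combining it with a scale that rates the site.

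**Conclusion.** The point holds as a defect in a stated rule: the scored item does not match the study's target, and the rule permits a positive MRI with no visible abnormality. The call goes straight into the primary outcome. It is not a demonstrated bias, because the frequency s is not in the documents and may be small.

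The loss of 1.5 to 7.5 points from a 15-point gain, for s between 10% and 50%, rests on three assumptions: visible-lesion rates of 0% and 15%, the same s on both scans, and (for the specificity ceiling) the same s in reference-negative patients.

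**What to change.** In the Image interpretation section:

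- Define the scored item as the likelihood that an epileptogenic structural abnormality is visible on these images.
- Allow a score of 3 or above only when the reader names a visible abnormality and records its location.
- Require a score of 1 or 2 when none is seen, whatever the clinical suspicion.

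Readers may still know the history. The change should be made before reading starts, since image-driven and history-driven scores could not be separated afterwards without reading the scans again.

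The cost is a rewritten paragraph and one extra field on the reading form, with no additional scans, readers or patients. Observed sensitivities will be somewhat lower. A reader who knows the site may still over-read subtle change there, so this influence is reduced and not eliminated.
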